4.5.2 Clinical Adverse Events

Treatment-emergent AEs (TEAEs)

All AEs will be analyzed based on the principle of treatment emergence. A treatment-emergent AE was defined as an AE that started or worsened after the start of first infusion of study treatment.

To define treatment emergence for AEs with missing start or stop date or time the following additional criteria will be used:

- if both the start and stop dates for a particular AE are missing, then that AE is considered treatment emergent;
- if the start date for a particular AE is missing and the stop date/time falls after the first dose date/time, then that AE is considered treatment emergent;
- if the start date for a particular AE was the same as the first dose date, and the start time was missing, then that event is considered treatment emergent.

For AEs with a partial start date, the year/month of the event date will be compared to that of the first dosing date to determine whether the event is treatment emergent.

In addition, SAEs that occurred since a subject was screened in the study and prior to the first infusion of study treatment, which by definition are not treatment-emergent, will be analyzed separately.

Only TEAEs will be included in the AE tables, unless otherwise specified. Listings of AEs will include all events, whether treatment-emergent or not.

As specified in the protocol, subjects were expected to return to the study site for an End of Study visit 18 weeks after the last administration of study treatment. However, some subjects may elect to continue study participation on a modified schedule after discontinuing treatment, possibly in substantial excess of 18 weeks. For most general AE summaries, AEs

Final V1.0

with an onset more than 18 weeks after the last dose will be excluded (will specify in the footnote of the specific table). For incidence rate analyses excluding AEs more than 18 weeks after the last dose, the "last day on study" in follow-up time calculation will be replaced with "18 weeks after last dose or last day on study, whichever earlier". Summaries of deaths and AEs leading to study withdrawal, and other selected analyses will include all AEs regardless of the time since the last dose. Listings will include all AEs, unless otherwise specified.

4.5.2.1 Summary and incidence analysis

Overall summary of AE table will summarize the number of subjects with any AE, with any AE by maximum severity, the number of subjects with any related AE (related to study drug as assessed by investigator), the number of subjects with SAE, the number of subjects with related SAE, the number of subjects with AE leading to study drug discontinuation, the number of subjects with AE leading to study withdrawal, and the number of deaths. This table will be done by treatment group as well as by treatment group stratified by ApoE status.

The sorting order for AE incidence tables, unless otherwise specified, will be by decreasing frequency order of "BIIB037 total" column within each category in the tables presented by treatment group, and by decreasing frequency order of "BIIB037 high dose total" column within each category in the tables presented by treatment group stratified by ApoE status. A subject is counted only once within each category in each table. For example, for the table of AEs by system organ class and preferred terms sorted by decreasing frequency presented by treatment group, system organ class will be presented in decreasing frequency order of BIIB037 total column, and within each system organ class, preferred terms will be presented in decreasing frequency order of BIIB037 total column. A subject is counted only once within each system organ class and preferred term.

The following AE incidence tables will be provided (presented both by treatment group and by treatment group stratified by ApoE status, unless otherwise specified):

- 1. AEs by system organ class and preferred term sorted by decreasing frequency
- 2. AEs by system organ class and preferred term sorted by alphabetical order (by treatment group)
- 3. AEs by system organ class, high level group term and preferred term (by treatment group only)
- 4. AEs by system organ class (by treatment group)
- 5. AEs with at least 2% higher in incidence for either low or high dose compared to placebo by system organ class and preferred term
- 6. AEs by preferred term
- 7. AEs with an incidence of 5% or more in any treatment group by preferred term
- 8. Severe AEs by system organ class and preferred term (by treatment group)
- 9. Severe AEs by preferred term
- 10. AEs by maximum severity by system organ class and preferred term (by treatment group) (System organ class will be presented alphabetically. Preferred terms will be presented in decreasing frequency order. Maximum severity will be presented within each preferred term in the order of mild, moderate, severe, unknown and total. A

Final V1.0

subject will be counted only once at the maximum severity within each system organ class and preferred term.)

- 11. AEs by maximum severity by preferred term (by treatment group) (Preferred terms will be presented in decreasing frequency order. Maximum severity will be presented within each preferred term in the order of mild, moderate, severe, unknown and total. A subject will be counted only once at the maximum severity within each preferred term.)
- 12. Related AEs by system organ class and preferred term
- 13. SAEs by system organ class and preferred term
- 14. SAEs by preferred term
- 15. Related SAEs by system organ class and preferred term
- 16. AEs that led to discontinuation of study treatment by system organ class and preferred term
- 17. AEs that led to withdrawal from study by system organ class and preferred term
- 18. SAEs with fatal outcome by system organ class and preferred term
- 19. AEs that occurred within 2 hours from infusion start by system organ class and preferred term (by treatment group)
- 20. AEs by12 weeks intervals from first infusion to the end of study by system organ class and preferred term (by treatment group)
- 21. Pre-treatment SAEs that occurred since screening and prior to first infusion by system organ class and preferred term

The following listings will be provided.

- 1. Listing of AEs
- 2. Listing of SAEs
- 3. Listing of AEs that led to discontinuation of study treatment
- 4. Listing of AEs that led to withdrawal from study
- 5. Listing of AEs that occurred within 2 hours from infusion start
- 6. Listing of AEs related to PET ligands
- 7. Listing of SAEs with fatal outcome
- 8. Listing of AEs for subjects with treatment-emergent positive anti-BIIB037 antibody

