3 SAMPLE SIZE JUSTIFICATION

The study's sample size is based, in part, on results from a protocol-specified interim analysis from Study 221AD103 which included 1 year data from 1, 3 and 10 mg/kg treatment groups.

A sample size of 450 subjects per treatment group (1350 in total) was planned to have approximately 90% power to detect a true mean difference of 0.5 in change from baseline CDR-SB at Week 78 between the 2 treatment groups. This power calculation was based on a 2-sided t-test assuming equal variance with a final significance level of 0.05, a standard deviation (SD) of 1.92 and a drop-out rate of 30%. The SD estimate of 1.92 for Week 78 reflected a 39% increase over the SD from the protocol-specified interim analysis of 1-year data.

The assumed true mean difference of 0.5 between the 2 treatment groups represents an approximately 25% reduction in the placebo mean change from baseline at Week 78 if the placebo mean change is estimated to be 2.

As defined in the protocol, the sample size for this study (and for the identically designed Study 221AD302) was reassessed in a blinded manner in November 2017 (approximately 3 months before enrollment completion and with about 10.6% of the data available on the primary endpoint from Studies 221AD301 and 221AD302 combined). At this timepoint, the SD of the primary endpoint was estimated based on the pooled blinded data from two studies using a modified version of Gould-Shih simple-adjustment one sample variance (Zucker et al. 1999):

$$s_{adj}^2 = s_{os}^2 - \frac{2N}{9(N-1)}\delta^2,$$

where N denotes the number of subjects included in the analysis for blinded sample size reestimation (subjects with both baseline and Week 78 CDR-SB available at the time of sample size re-estimation), δ is the assumed true treatment effect (same treatment effect assumed for both the high dose group and low dose group in this analysis), and s_{os}^2 is the unadjusted one sample variance of the primary endpoint estimate from the pooled blinded data.

As a result of this analysis, the sample size has been increased from 1350 to 1605 (450 to 535 per treatment group) to assure adequate power for detecting a mean treatment effect of 0.5.

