4 STATISTICAL ANALYSIS METHODS

4.1 General Considerations

This statistical analysis plan (SAP) only covers the analyses for the primary, secondary and tertiary objectives for the placebo-controlled portion of the study. Hereafter, the placebo-controlled portion of the study will be referred to as "the study" in the rest of this SAP (e.g.,

Final V1.0

completion of the study means completion of the placebo-controlled portion). A separate SAP will be prepared for the analyses of the LTE period and integrated analyses across both portions of the study. The analyses of additional exploratory endpoints will be documented separately.

Summary tables will be presented using descriptive summary statistics. For continuous variables, summary statistics will generally include: number of subjects with data, mean, standard deviation, median, 25% percentile, 75% percentile, minimum and maximum. For categorical variables, this will generally include: number of subjects randomized or dosed, number with data, and the percent of those with data in each category.

There are two types of analysis displays for tables: by treatment group (analysis display A in Appendix 6.1) and by treatment group stratified by ApoE status (analysis display B in Appendix 6.1; here ApoE status refers to the status recorded in IXRS [see Table 1 for correspondence between treatment groups and treatment groups stratified by ApoE status]). The analysis display for each analysis will be defined in each section. All the listings will be presented by treatment group stratified by ApoE status, unless otherwise specified.

Unless otherwise specified, baseline value is defined as the most recent non-missing measurement collected prior to the first dose. Change from baseline will be defined as post-baseline value minus baseline value.

Unless stated otherwise, all statistical tests will be 2-sided with statistical significance level of 0.05.

The statistical software, SAS® will be used for all summaries and analyses.

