4.1.1 Analysis Population

- Intent-to-treat (ITT) population: The Intent-to-treat population is defined as all randomized subjects who received at least one dose of study treatment (aducanumab or placebo).
- Per-protocol (PP) population:

The per-protocol population is defined as all subjects in the ITT population and also

- o had no violations of the following inclusion criteria:
 - Must have at least 6 years of education or work experience to exclude mental deficits other than MCI or mild AD;
 - Must have a positive amyloid PET scan;
 - Must have:
 - A CDR-Global Score of 0.5;
 - A Repeatable Battery for Assessment of Neuropsychological Status (RBANS) score of 85 or lower indicative of objective cognitive impairment (based upon the Delayed Memory Index score);
 - An MMSE score between 24 and 30 (inclusive).
- o had at least 14 infusions.
- o did not make any change to concomitant AD symptomatic medications during the study.

Final V1.0

- ¹⁸F-florbetapir amyloid PET analysis population:
 - The ¹⁸F-florbetapir amyloid PET analysis population is defined as all randomized subjects who received at least one dose of study treatment (aducanumab or placebo), used ¹⁸F-florbetapir ligand for amyloid PET scan, and had an evaluable baseline amyloid PET SUVR value for the composite region-of-interest using cerebellum as the reference region.
- ¹⁸F-flutemetamol amyloid PET analysis population (applicable only to Japan): The ¹⁸F-flutemetamol amyloid PET analysis population is defined as all randomized subjects who received at least one dose of study treatment (aducanumab or placebo), used ¹⁸F-flutemetamol ligand for amyloid PET scan, and had an evaluable baseline amyloid PET SUVR value for the composite region-of-interest using cerebellum as the reference region.

• Safety population:

The safety population is defined as all randomized subjects who received at least one dose of study treatment (aducanumab or placebo). It is the same population as the ITT population.

• Safety MRI population:

The safety MRI population is defined as all randomized subjects who received at least one dose of study treatment (aducanumab or placebo) and had at least one post-baseline MRI assessment.

• PK analysis population:

The PK analysis population is defined as all randomized subjects who received at least one dose of study treatment (aducanumab or placebo) and had at least one measurable aducanumab concentration in serum.

• Immunogenicity population:

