4.5 Safety Analysis

4.5.1 General Considerations

Analysis population

Safety population will be used for safety analyses of AEs, clinical laboratory data, Columbia Suicide Severity Rating Scale (C-SSRS) data, ECG data and vital sign data (all the safety data except for ARIA data). Safety MRI population will be used for analyses of ARIA data.

Final V1.0

Safety treatment groups

Different from the randomization treatment groups, if a subject who was randomized to placebo group accidentally received one or more doses of the active treatment during the study, he/she will be classified as either low or high dose group for all the safety analyses, depending on the ApoE status and the maximal dose level of the active treatment received (Table 5). A listing of such subjects will be provided, as described in section 4.2.5. Safety treatment groups will be the same as the randomization treatment groups for other subjects (subjects randomized to active treatment groups, and subjects randomized to placebo without any accidental active dose). Safety treatment groups will be used for all the safety analyses unless otherwise specified.

Table 5: Safety treatment groups for placebo subjects with accidental active treatment

Randomization treatment group	Randomization ApoE status	Safety treatment group classification based on the maximum dose level of the accidental active treatment		
		>0 to 3 mg/kg	>3 to 6 mg/kg	>6 mg/kg
Placebo	ΑροΕ ε4 (+)	Low dose	High dose	High dose
	ΑροΕ ε4 (-)	Low dose	Low dose	High dose

Safety analysis displays

AEs, clinical laboratory data, C-SSRS data, ECG data and vital sign data (all the safety data except for ARIA data) will be summarized by treatment group (placebo, low dose, high dose and BIIB037 total; analysis display A in Appendix 6.1), unless otherwise specified. All the ARIA related tables will be presented by treatment group stratified by ApoE status (3 columns under each treatment group: ApoE ϵ 4+, ApoE ϵ 4- and total; analysis display B in Appendix 6.1), unless otherwise specified. A subset of AE tables will also be presented by treatment group stratified by ApoE status in addition to by treatment group. All the listings will be presented by treatment group stratified by ApoE status.

Incidence, incidence proportion and incidence rate

Incidence and incidence proportion will be provided in incidence tables. Incidence is
defined as the number of subjects who experienced an event. Incidence proportion is

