defined as the number of subjects who experienced an event divided by total number of
subjects in the analysis population, i.e., percentage. Each subject will be counted only
once within each category.

Final V1.0

- Incidence and incidence rate will be provided in incidence rate tables. Two different kinds of incidence rate tables will be provided as appropriate for different analyses. Definitions are provided below.
 - (1) Follow-up adjusted incidence rate defined as the number of subjects who experienced an event divided by the total of entire follow-up time among the subjects in the analysis population. The entire follow-up time for a subject is defined as the time from the first dose until the last day on study. Each subject will be counted only once within each category.
 - (2) Exposure-adjusted incidence rate (EAIR) defined as the number of subjects who experience an event divided by the total exposure adjusted follow-up time among the subjects in the analysis population. The exposure adjusted follow-up time is defined as the time from the first dose until the initial occurrence of the event for those who experienced an event, or from the first dose until the end of follow-up (the last day on study) for those who did not. Each subject will be counted only once within each category.

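### The AE table by 12-week interval falls under a whole-population denominator, so percentages in later intervals are diluted by subjects no longer observed

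*SAP*

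**What the plan says.** Section 4.5.2.1 of the placebo-controlled SAP opens its list with "The following AE incidence tables will be provided (presented both by treatment group and by treatment group stratified by ApoE status, unless otherwise" specified. Item 20 in that list is "AEs by12 weeks intervals from first infusion to the end of study by system organ class and preferred term (by treatment group"), and no denominator is attached to it.

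Section 4.5.1 sets the rule for such tables: "Incidence and incidence proportion will be provided in incidence tables". Incidence proportion is "defined as the number of subjects who experienced an event divided by total number of" "subjects in the analysis population, i.e., percentage". For AEs the analysis population is the safety population, and section 4.1.1 puts no at-risk condition on it: "The safety population is defined as all randomized subjects who received at least one dose of study treatment (aducanumab or placebo").

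Section 4.1 limits this SAP to the placebo-controlled part: "completion of the study means completion of the placebo-controlled portion". For LTE entrants, section 4.3.1 (visit windows) ends that period on the day before the first LTE infusion. Section 2.1 puts this at about Week 80 (76 weeks of treatment plus 4). Other subjects are followed for about 18 weeks after the final dose, to about Week 94. Section 4.5.2 drops AEs starting more than 18 weeks after the last dose from most general summaries, but shortens follow-up time to match only in incidence rate analyses.

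**The concern.** A fixed denominator is sound for a whole-period percentage. Split into consecutive 12-week intervals, the same denominator keeps every dosed subject in each interval, including those who can no longer contribute an event to it. A constant true risk then appears to fall with time on study. A reader who takes the columns as interval risks would conclude that late AEs are rarer than they are, and the error runs towards apparent safety. Where the 18-week cut-off is applied, subjects who stop treatment but stay in the study lose their later events from the numerator and remain in the denominator.

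**Working it through.** **The plan's own figure.** The SAP states no number for item 20. The only drop-out figure is in section 3 ("a drop-out rate of 30"%). It reproduces: with difference 0.5, SD 1.92, two-sided 0.05 and 90% power, n = 2 × 1.92² × (1.960 + 1.282)² / 0.5² = 310 evaluable per group, and 310 / 0.70 = 443, close to the stated 450. With 450 × 0.70 = 315 evaluable, power is 90.5%. The 30% is therefore a genuine planning input, although it was set for the Week 78 endpoint.

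**Inputs for the check**
- Drop-out of 30% by Week 78 (section 3), taken here as loss to AE observation. This is an assumption.
- Constant hazard, so the share observed at week t is S(t) = 0.7^(t/78). This is an assumption; a linear pattern is shown beside it.
- LTE entrants leave at Week 80 and all others at Week 94 (section 2.1), with no further loss between Weeks 78 and 94.
- LTE uptake L among those remaining is not given in the SAP, so it is varied.

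**Dilution factor.** Shown percentage / true interval risk = mean of S(t) over the interval. It does not depend on the size of the risk.

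| Weeks | Mean share, constant hazard | Mean share, linear | A true 5% per 12 weeks shows as (constant hazard) |
|---|---|---|---|
| 1-12 | 0.973 | 0.977 | 4.87% |
| 13-24 | 0.921 | 0.931 | 4.61% |
| 25-36 | 0.872 | 0.885 | 4.36% |
| 37-48 | 0.825 | 0.838 | 4.13% |
| 49-60 | 0.781 | 0.792 | 3.91% |
| 61-72 | 0.740 | 0.746 | 3.70% |

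In Weeks 61-72 the shortfall is 1 − 0.740 = 26%. With 20% or 35% drop-out instead, the share at mid-interval (Week 66) is 0.80^(66/78) = 0.83 or 0.65^(66/78) = 0.69, so the range is roughly 17% to 30% too low.

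**After Week 72.** The mean of S over Weeks 72-78 is 0.710.
- Weeks 73-84: [6 × 0.710 + 2 × 0.70 + 4 × 0.70 × (1 − L)] / 12. This gives 0.705 at L = 0, 0.588 at L = 0.5 and 0.495 at L = 0.9.
- Weeks 85-96: 10 × 0.70 × (1 − L) / 12. This gives 0.583, 0.292 and 0.058 respectively.

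**Between arms.** With equal drop-out and LTE entry the dilution cancels in a ratio, while absolute differences shrink by the same factor as the percentages. With 35% drop-out on high dose and 25% on placebo (an illustration only), the Weeks 61-72 ratio is multiplied by (0.65/0.75)^(66/78) = 0.886, or 11% too low.

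**Does a start-of-interval denominator cure it?** Not after Week 72. At Week 72 the share is 0.719 (about 385 of 535 per group). For Weeks 73-84, 0.588/0.719 = 0.82 and 0.495/0.719 = 0.69, so percentages stay 18% to 31% too low at L = 0.5 to 0.9. For Weeks 85-96, follow-up ends after 10 of the 12 weeks, leaving about 17%.

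**The case against.** The denominator for item 20 is inferred. The item is one line among 21, and the section 4.5.1 definition is generic. Section 4.1 says categorical summaries generally use the percent of those with data, and section 3.1.2 of the LTE SAP lets the analysis period help decide who is in an output. A table shell could print an at-risk number. A percentage of all dosed subjects is also a legitimate description if it is labelled as such. None of this displaces the rule: section 4.1 is a general convention, section 4.5.1 is specific to incidence tables, the LTE SAP governs other outputs, and this SAP mentions no at-risk number for item 20.

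Mitigation does exist. Section 4.2.1 plans counts of discontinuation and withdrawal by time band, with Kaplan-Meier plots. Section 4.5.2.2 gives follow-up adjusted rates. Sections 4.5.3.4 and 4.5.3.5 give exposure-adjusted rates and Kaplan-Meier curves with numbers at risk for ARIA-E. This limits the consequence. However, the section 4.5.2.2 rates cover the whole period and cannot show late risk for general AEs.

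A reader might go further and infer that the table biases the comparison with placebo in the drug's favour. The documents do not support that: they give no drop-out or LTE uptake by arm, and with equal losses the ratio is intact. Nor do they state that the table is meant to track risk through titration to the target dose. Dose 7 falls at about Week 24, and the shares on either side of it, 0.921 and 0.872, differ only modestly.

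**Conclusion.** The point holds as a minor one. The SAP's stated rule, applied to an interval table, gives a misleading time pattern within each arm. The size rests on reading the 30% planning allowance as loss to AE observation. On that reading the two drop-out shapes agree closely: 26% too low in Weeks 61-72 at constant hazard and 25% if linear. Beyond Week 80 the direction is certain but the size is not, because it depends on LTE uptake. The last interval could range from a little over half the true value with no LTE entry to about 6% of it with 90% entry. No efficacy conclusion, whole-period AE rate, disposition summary or ARIA-E time analysis is touched.

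**What to change.** For item 20 only, report subjects with an event in the interval divided by person-time under AE observation in the placebo-controlled period during that interval. Truncate person-time at LTE entry, at study exit and, where that cut-off is used, at 18 weeks after the last dose. This is the follow-up adjusted rate of section 4.5.1 restricted to an interval. Print the number under observation at the start of each interval at the head of its column.

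If a percentage is kept, divide by the number at interval start, end the last percentage interval before transfer to the LTE (about Week 80), and show later events as counts or person-time rates.

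The cost is a short addition to the SAP and a change to one table program. Late-interval estimates will be less precise, because they rest on fewer observed subjects.
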